6.1. Statistical Definitions and Algorithms

6.1.1. Baseline

The last observation recorded before the first dose of lixivaptan during Lixivaptan Titration Period will be used as the baseline observation for all calculations of change from baseline unless otherwise specified.

6.1.2. Treatment Group and Cohort

For Part 1 summaries after randomization, the analysis results will be presented by two treatment groups: lixivaptan and Placebo.

Since all participants in Part 2 are treated with lixivaptan, the summaries for Part 2 will be

presented in the following treatment cohorts and overall (treatment cohorts combined):

- Part1/Part2 Placebo/Lixivaptan: all participants in Part 2 who were randomized into Placebo treatment group in Part 1
- Part1/Part2 Lixivaptan/Lixivaptan: all participants in Part 2 who were randomized into lixivaptan treatment group in Part 1

6.1.3. Multiple Comparisons

To control the family-wise type I error at the pre-specified level (≤ 0.01), the primary and secondary endpoints in Part 1 will be tested in hierarchical order:

- Treatment difference for the primary endpoint must be statistically significant (p-value ≤ 0.01)
- Treatment difference for annualized rate of change (slope) in on-treatment eGFRs is tested only if treatment difference for the primary endpoint is statistically significant (p-value ≤ 0.01)
- Treatment difference for annualized percent change from baseline in htTKV is tested only if treatment difference for annualized rate of change (slope) in on-treatment eGFRs is statistically significant (p-value ≤ 0.01)

Because the testing is sequential, the type I error rate of ≤ 0.01 is maintained. Failure at any stage in the sequence implies automatic failure at all subsequent stages. All p-values for each comparison without adjustments will be provided in the summary tables for informational purposes.

No adjustments will be made for multiple comparisons for other endpoints.

6.1.4. Handling of Dropouts or Missing Data

Assessments are planned, by protocol, to be collected from all randomized participants except those who 1) withdraw consent AND 2) do not consent to any collection of data. Every effort will be made to keep randomized participants in the study and offer them options for continued treatment and, at a minimum, continued study participation to the degree possible; strategies of these efforts are described in the study protocol Section 4.2.4, Section 4.2.7, and Appendix 5 (Section 13.5) in order to minimize missing data. While all possible efforts will be made to ensure that participants stay in the study and all data is collected as scheduled, the occurrence of missing data cannot be completely eliminated.

The handling of missing data is dependent upon the efficacy analyses (see Section 8 Efficacy Analysis for detail). The missing data for efficacy analyses are generally imputed by the following methods:

• Missing at random (MAR) – mixed-effects model for repeated measures (MMRM): a modeling approach (missing data are not imputed prior to the analysis)

- Missing at random (MAR) multiple imputation (MI)
- Missing not at random (MNAR) multiple imputation (MI) with assumptions of missing not at random. Treatment impact on efficacy endpoints for missing data varies independently on the two treatment arms bi-dimensionally. Pattern-mixture approach is applied to investigate the MNAR pattern based on dropout reasons. Specifically, MNAR in the following patterns of dropout reasons will be investigated as MNAR:
 - Lack of efficacy (LOE)
 - LOE and adverse events (AE)
 - All dropouts

6.1.4.1. Multiple Imputation Methods

MI is a simulation-based approach where missing values are replaced using an appropriate stochastic model given the observed data and covariates, creating multiple completed data sets. These completed datasets (observed data and imputed data) are then analyzed using pre-specified analysis methods, and the different parameter estimates across the datasets are then combined to produce unique point estimates, standard errors, confidence intervals, and p-value taking into account the uncertainty of the imputation process.

The following 2 MI analysis models, one based on the standard MAR imputation approach and the other based on the MNAR imputation approach, will be used to examine robustness of the primary analysis results.

6.1.4.1.1 Standard MAR Imputation

The MAR imputation model will impute missing values using a regression-based multiple imputation model (Little et al, 1996). A by-treatment multiple regression model will be fit that includes the observed outcome at that visit as the dependent variable. The independent variables will generally include baseline value, sex, age, randomization stratification factors, and treatment duration of study drug unless otherwise specified. Using these regression models, a missing value for a participant will be imputed as a draw from the predictive distribution. This process will be repeated 50 times, resulting in 50 complete analysis data sets. The analysis has the following steps:

- Using Monte Carlo Markov Chain (MCMC) methodology from SAS PROC MI by treatment group to impute the missing data to obtain 50 complete analysis data sets
- Using the pre-specified analysis to analyze each set of the completed data along with the imputed data
- Obtaining the overall results using PROC MIANALYZE

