6.4 Double-blind, Randomized Treatment Period

The Double-blind Randomized Treatment Period will last 52 weeks, and visits will occur every 4 weeks \pm 5 days (Visit 10 to Visit 22).

6.4.1 Visits 10 to 21

Visits 10 to 21 will occur every 4 weeks \pm 5 days. Visits 10, 11, 13, 14, 16, 17, 19, 20 and 21 may be conducted remotely by an HHC/qualified site personnel (with the agreement of the participant and the discretion of the investigator and where available and locally approved by the CA and/or IRB/EC). Visits 12, 15, and 18 must be conducted in the clinic. The following procedures will be performed at each visit unless otherwise noted:

- Provide participant with a urine collection container and written instructions to produce a first morning, fasting (\geq 8 hours, except for water) urine specimen to be brought in at Visit 15 for assessment of urine osmolality.

- Process urine specimen collected by participant as a fasting AM urine specimen the morning of Visit 15 only for determination of urine osmolality.
- Review and assess AEs and SAEs.
- Collect and review new concomitant medication information.
- Collect and review any acetaminophen use information.
- Review and assess laboratory test results.
- Collect medical resource utilization data since the last visit (i.e., medication use or changes; unplanned office visits; urgent care or emergency department usage and hospitalizations) based on any AEs/SAEs reported.
- Perform study drug reconciliation and review study drug compliance.
- Check vital signs.
- Perform a urine pregnancy test for WOCBP (Visit 12, Visit 15, and Visit 18 only).
- Perform a brief physical examination (Visit 15 only or if indicated by signs or symptoms).
- Perform a 12-lead ECG (Visit 15 only).
- Collect blood samples for the following laboratory testing:
 - chemistry (Visit 12, Visit 15, and Visit 18 only);
 - serum sodium (all visits); assessed as part of chemistry at Visits 12, 15 and 18 and as part of liver chemistry at all other visits;
 - liver chemistry;
 - serum creatinine for eGFR determination;
 - hematology (Visit 15 only);
 - sparse PK sampling (Visit 12 (pre-dose), Visit 15 (1 to 6 hrs post-dose), and Visit 18 (6 to 10 hrs post-dose) only and in accordance with sparse PK sampling schedule ([Schedule of Procedures – Part 1](#))).

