8.4.2 Sensitivity Analysis of the Primary Efficacy Analysis

In particular, in order to address the impact of missing data on the results from the primary efficacy analysis, a number of sensitivity analyses will be performed. The detailed sensitivity analyses for the primary efficacy analysis will be described in the statistical analysis plan (SAP).

Amongst these sensitivity analyses, the main sensitivity analysis of the primary efficacy analysis will use the mean of eGFR values obtained pretreatment and the mean of eGFR values obtained off treatment after the end of the 52-week treatment period, regardless of adherence to randomized treatment and/or withdrawal for all randomized participants, i.e., Intent-To-Treat participants. Missing values at Week 52 will be imputed using multiple imputations (assuming missing at random). Tipping point analyses will be included using a pattern-mixture model to impute missing data at Week 52 (assuming missing not at random) by systematically varying assumptions about the missing outcomes on the two treatment arms – these tipping point analyses will be bi-dimensional, i.e., allow the assumptions about the missing outcomes in the two arms to vary independently, and will include scenarios where the dropouts on the lixivaptan arm have worst outcome compared to placebo dropouts.

8.5 Secondary Efficacy Analyses.

If the primary efficacy analysis is statistically significant at the 1% level of significance, then the secondary efficacy endpoints of (1) annualized rate of change (slope) in eGFR based on all on-treatment eGFR determinations during the Double-blind, Randomized Treatment Period calculated from the CKD-EPI_{cr}_R equation for serum creatinine; and (2) annualized change in TKV as measured by MRI will be analyzed. Each will be tested at the 1% level of significance in sequential order using a closed testing procedure on the SEAS. The details of the testing procedure will be provided in the SAP for the study.

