8.2.1. Sensitivity Analyses of the Primary Efficacy Endpoint

8.2.1.1. Primary Sensitivity Analyses

Sensitivity analyses on the primary efficacy endpoint will be performed using the same ANCOVA model as the primary efficacy analysis with fixed effects for treatment group and the randomization stratification factors (CKD stage [CKD2 versus CKD3/4] and Mayo Clinic ADPKD Image Classification [1C, 1D, or 1E]) and the baseline eGFR as a covariate.

Two sensitivity analyses will be performed on the mITT:

- The annualized change in eGFR (2021 CKD-EPIcr_R) without restriction from baseline to off treatment assessment after Week 52 (mean of 3 eGFR values obtained during off-treatment follow-up visits after Week 52); missing data are handled by multiple imputation:
 - MAR (Section 6.1.4.1.1)
- The annualized change in eGFR (2021 CKD-EPIcr_R) with restriction from baseline to final assessment (mean of 3 eGFR values obtained during Follow-up Period I after Week 52 for on-treatment completers or, for participants who discontinue study drug treatment prior to Visit 22, during the Follow-up Period 8 to 28 days following study drug treatment discontinuation); missing data are handled by multiple imputation:
 - MAR (Section 6.1.4.1.1)
 - MNAR and tipping point analysis (Sections 6.1.4.1.2 & 6.1.4.1.3)

Two sensitivity analyses will be performed on the PEAS:

- The annualized change in off-treatment eGFR (2021 CKD-EPIcr_R) without restriction from baseline to final assessment (mean of 3 eGFR values obtained during Follow-up Period I after Week 52 for on-treatment completers or, for participants who discontinue study drug treatment prior to Visit 22, during the Follow-up Period 8 to 28 days following study drug treatment discontinuation)
- The annualized change in eGFR (2009 CKD-EPI) with restriction from baseline to final assessment (mean of 3 eGFR values obtained during Follow-up Period I after Week 52 for on-treatment completers or, for participants who discontinue study drug treatment prior to Visit 22, during the Follow-up Period 8 to 28 days following study drug treatment discontinuation)

One sensitivity analysis will be performed on the on-treatment completers of the PEAS :

• The annualized change in eGFR (2021 CKD-EPIcr_R) without restriction from baseline to final assessment (mean of 3 eGFR values obtained during Follow-up Period I after Week 52 for on-treatment completers or, for participants who discontinue study drug

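### The MAR imputation model for the eGFR sensitivity analyses leaves out the on-treatment and post-discontinuation eGFR already collected, and can bias them if dropout follows observed decline

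*SAP*

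**What the plan says.** SAP 6.1.4.1.1 fits the imputation separately in each arm: "A by-treatment multiple regression model will be fit that includes the observed outcome at that visit as the dependent variable". Its predictors are: "The independent variables will generally include baseline value, sex, age, randomization stratification factors, and treatment duration of study drug". The sentence ends with a proviso that leaves room for a different list, but SAP 8.2.1.1 does not use it. For the analysis "without restriction from baseline to off treatment assessment after Week 52" it says that "missing data are handled by multiple imputation", points back to 6.1.4.1.1 and adds no predictor. Where the authors wanted an endpoint-specific list, for htTKV in SAP 8.3.2, they wrote one.

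Protocol 8.4.2 gives this Week 52 analysis its standing: "the main sensitivity analysis of the primary efficacy analysis will use the mean of eGFR values obtained pretreatment" together with the off-treatment mean after the 52-week period, whatever the adherence. The second mITT analysis in SAP 8.2.1.1 uses each early stopper's own off-treatment values. It applies the same MAR model to those who have none, then MNAR and tipping-point analyses.

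The omitted data are scheduled. Protocol 6.4.1 states "Visits 10 to 21 will occur every 4 weeks" and lists serum creatinine for eGFR at each of these visits. With Visit 22 that makes the 13 visits of the slope MMRM in SAP 8.3.1. Randomized participants who stop drug early also give three off-treatment samples between Day 8 and Day 28 (Protocol 4.2.4), and the primary analysis relies on them (SAP 8.2).

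**The concern.** Missing at random is an assumption conditional on what is in the model. If the chance of leaving depends on the eGFR decline seen so far, it can hold given the on-treatment values and fail given only baseline, demographics, strata and duration. Fast decliners who leave are then imputed too favourably. A participant who stops at Week 20, gives three off-treatment samples and then leaves has Week 52 imputed without any of those measurements.

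The plan itself treats such dropout as possible. Lack of efficacy is a listed discontinuation reason (Protocol 4.2.5) and a named MNAR pattern (SAP 6.1.4). Post-randomization eGFR is not among the results that SAP 3.5 withholds from sites and participants.

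At stake is the credibility of the main robustness check. The MNAR step (SAP 6.1.4.1.2) starts from imputations made with the same model and shifts them by multiples of the MAR treatment difference, so both its starting point and its step size inherit any bias.

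**Working it through.** **Design figure.** From SAP 3.7: SD 6.20, difference 1.40, alpha 0.01, power 90%, ratio 2:1. Placebo n = (1 + 1/2)(2.576 + 1.282)² × 6.20²/1.40² = 1.5 × 14.88 × 19.61 ≈ 438. The total is 3 × 438 = 1314, as stated, which confirms a two-sided test. The documents give no figure for imputation bias, no dropout rate by arm and no relation between dropout and decline.

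**Assumptions.** Dropout is 12% on lixivaptan and 6% on placebo unless stated. At 2:1 this is (2 × 12% + 6%)/3 = 10% overall, in line with the 90% expected to enter Part 2. Correlation between on-treatment change and final off-treatment change: 0.3 to 0.7. Odds ratio for dropout: 1 to 3 per SD of faster decline. Share of dropouts retrieved with a Week 52 value: 0% or 50%, at random.

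**Size within an arm.** Let p be the fraction missing and d the distance by which the true mean of the missing lies below the arm mean. If the predictors cannot separate dropouts from others, the arm mean is too high by p·d/(1 − p). For lixivaptan at odds ratio 2 and correlation 0.5, d = 1.78, so 0.12 × 1.78/0.88 = 0.24. Simulation (600,000 per arm) gives 0.245. The placebo arm gives 0.126, so the difference is biased by 0.245 − 0.126 = 0.12.

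**Bias in the treatment difference with the SAP predictors** (positive favours lixivaptan; correlation 0.5 unless stated):

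| Dropout, lixivaptan / placebo | Link to decline | None retrieved | 50% retrieved at random |
|---|---|---|---|
| 12% / 6% | none | about 0 | about 0 |
| 12% / 6% | odds ratio 1.5 to 3, correlation 0.3 to 0.7 | +0.05 to +0.24 | +0.01 to +0.03 |
| 12% / 6% | odds ratio 2 | +0.12 | +0.01 |
| 20% / 10% | odds ratio 2 | +0.19 | +0.02 |
| 10% / 10% | odds ratio 2 | about 0 | about 0 |
| 7% / 16% | odds ratio 2 | −0.17 | −0.02 |
| 12% / 6% | placebo only, odds ratio 2 | −0.12 | −0.01 |
| 12% / 6% | slower decliners leave lixivaptan (odds ratio 0.5) | −0.24 | −0.03 |

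As a share of the planned effect, 0.046/1.40 = 3% and 0.244/1.40 = 17%. Adding a single on-treatment change variable brings the bias to 0.01 or less in absolute value in every row, but this simulation does not model when that value was taken.

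**Retrieval that is not random.** With half of average-decline dropouts retrieved and the chance of retrieval doubling per SD of slower decline (12% / 6%, odds ratio 2, correlation 0.5), the bias is +0.10 with the SAP predictors. At 25% it is +0.11. With on-treatment eGFR added it is 0.00 in both.

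**Which form of predictor.** A further check (12% / 6%, odds ratio 2) gave +0.14 for the SAP model with no retrieval and +0.03 or less with 10% to 50% retrieved at random. Using only the last on-treatment change and its week left +0.06 to +0.12 when few dropouts were retrieved, and created up to 0.07 where the SAP model had no bias. Entering the values visit by visit gave 0.01 or less in every scenario.

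**The case against.** The strongest reply is that the harm is conditional and the plan already limits it. The documents name tolerability and aquaretic effects repeatedly as reasons to reduce or stop drug, and Protocol 4.2.5 says mild creatinine rises should not lead to withdrawal. Treatment duration is in the model and marks early stopping. Protocol 4.2.4 and 6.9 ask those who stop to complete all later visits, so some dropouts will supply Week 52 values. The primary ANCOVA uses each stopper's own decline, and the slope MMRM uses the on-treatment eGFR. All of this stands and limits the size.

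Three stronger readings are tempting and are not supported. A reader might infer that the omission favours whichever arm loses more participants. That needs dropout to follow faster decline to a similar degree in both arms; the table shows nil and reversed cases. A reader might infer that fast decliners are always imputed as average; with random retrieval, duration recovers most of the signal. A reader might also infer that the tipping-point analysis is defeated. Offsetting a bias b in a lixivaptan arm with 12% imputed needs k = b/(0.12 × 1.40), so 0.05 to 0.24 corresponds to roughly 30% to 143%, well inside the 0% to 500% grid. However, the SAP attaches that grid to the other mITT analysis, where only participants without any follow-up eGFR are imputed, so it does not cover the Week 52 analysis.

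Duration does not settle the matter. Its coefficient is poorly supported with few retrieved dropouts, and it misleads when those who return declined more slowly than those who do not.

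**Conclusion.** The point holds in a conditional form. The imputation model omits the most informative data available, and the sensitivity analyses can be biased when dropout depends on observed decline and differs between arms. The direction depends on who drops out. Under the assumed 12% versus 6% dropout, odds ratio 1.5 to 3 in both arms and no retrieval, the size is about 0.05 to 0.24 mL/min/1.73 m² (3% to 17% of 1.40). It is about nil if dropout is unrelated to decline or equal in both rate and link, and 0.01 to 0.03 with half of dropouts retrieved at random. These figures rest on rates, correlations, odds ratios and retrieval shares that the documents do not give. The primary ANCOVA is untouched. SAP Section 12 reports early termination with 5 participants randomized and no statistical analyses, so this concerns the plan as written.

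**What to change.** In SAP 6.1.4.1.1, for the eGFR analyses:

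- Keep imputation by treatment group, so that an acute drug effect on eGFR is handled within the arm.
- Add the on-treatment eGFR change at each scheduled visit, Weeks 4 to 52, as separate variables in the PROC MI MCMC model, using only values taken on drug as SAP 4.1.1.2 defines them.
- Add the off-treatment eGFR from 8 to 28 days after the last dose where available. This helps the Week 52 analysis. In the other mITT analysis, anyone with such a value is not missing, so only the on-treatment values add information.
- Do not use a single last value with its study week. When few dropouts are retrieved, nearly all observed cases have that value at Week 52, so the effect of an earlier week cannot be estimated.

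No new data are needed. The cost is a larger imputation model and slightly more code.

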6.1.4.1.2 MNAR Imputation

The MNAR imputation of missing data and data analysis are implemented as following:

- Using a standard MAR-based multiple imputation approach (See Section 6.1.4.1.1) to impute missing data to obtain 50 complete analysis data sets
- The imputed data for missing reason matching the MNAR pattern will be adjusted by the following:
 - If the participant is randomized in the lixivaptan group, the imputed value will be reduced by k (e.g., 50%) times the treatment difference (obtained using the MAR approach)
 - If the participant is randomized in the placebo group, the imputed value will be increased by 1 (e.g., 100%) times the treatment difference (obtained using the MAR approach)
 - k and l are independently determined
- Using the pre-specified analysis to analyze each set of the completed data along with the imputed data
- Obtaining the overall results using PROC MIANALYZE

6.1.4.1.3 Tipping Point Analysis

As a sensitivity analysis to the multiple imputation analysis as described above in Section 6.1.4.1.2, a tipping point analysis will be performed in order to determine the robustness of the primary efficacy analysis.

A tipping point is the inflection point at which the inference under the MNAR assumption changes substantially (i.e., the specific k and l in MNAR imputation to reverse the statistical significance).

Since the missing data with the MNAR pattern are imputed bi-dimensionally, the tipping point curve will be determined for each of MNAR patterns by the following:

• Let 1 = 0%, 10%, 20%, 30%, 40%, 50%, 60%, 70%, 80%, 90%, 100%, 125%, 150%, 175%, 200%, 250%, 300%, 350%, 400%, 450%, and 500%.

Note that:

- \circ 1 = 0% (imputed missing in placebo as MAR)
- \circ 1 = 100% (imputed missing in placebo as lixivaptan)
- For each l, search a tipping point k by implementing k=0%, 10%, 20%, 30%, 40%, 50%, 60%, 70%, 80%, 90%, 100%, 125%, 150%, 175%, 200%, 250%, 300%, 350%, 400%, 450%, and 500%. Report the analysis results at the tipping point when a tipping point is found; otherwise, report the analysis results for k=500% when a tipping point is not reached.

Note that:

- \circ k = 0% (imputed missing in lixivaptan as MAR)
- \circ k = 100% (imputed missing in lixivaptan as placebo)

• The tipping point curve consists of all the paired points of k and l when the tipping point is found.

6.1.5. Analysis Visit

Data summarized by study visit will be based on the nominal visit as reported on the eCRF.

Data collected at unscheduled visits will only be included in by-visit summaries if the data is missing at a visit and the date of an unscheduled visit is within the visit window by protocol. All data will be included in participant listings.

Visit 22 is referred to as the Week 52 visit in Part 1.

Visit 42 is referred to as the Week 104 visit in Part 2.

Early Termination (ET) visit is defined as the last visit either during the Double-blind, Randomized Treatment Period in Part 1 or during the Maintenance Treatment Period in Part 2 for participants who early terminated from study or early discontinued from study drug during that period in Part 1 or Part 2.

Visit 22/ET is defined as either Visit 22 or the ET visit in Part 1. Similarly, Visit 42/ET is defined as either Visit 42 or the ET visit in Part 2.

